8.2.1.6. Other Assessments

To adequately monitor for the risk of 5-HT3 antagonist pre-medication which may predispose subjects to arrythmias, a 24-hour telemetry monitoring for subjects with electrolyte abnormalities may be performed, if clinically indicated.

8.2.2. Efficacy/Anti-viral Activity Assessment

8.2.2.1. Clinical Evaluation to Assess Recovery

CONFIDENTIAL Page 41 of 66

Assessment of recovery at the time points described in the Schedule of Activities (see **Section 1.3**) is based on hospital discharge or normalization of fever, respiratory rate, alleviation of cough, and resolution of hypoxia. Normalization of fever (defined as $<36.6^{\circ}$ C from axillary site, or $<37.2^{\circ}$ C from oral site or $<37.8^{\circ}$ C from rectal or tympanic site), respiratory rate (<24 bpm while breathing room air), alleviation of cough (defined as mild or absent in a patient reported scale of 0=absent, 1=mild, 2=moderate, and 3=severe) and resolution of hypoxia (defined as SpO2 \ge 93% in room air or P/F \ge 300 mmHg) must be sustained for at least 48 hours.

8.2.2.2. **EQ-D5-5L**

Administration of questionnaires for patient-reported outcomes at the time points described in the Schedule of Activities. The 5-level EQ-5D version (EQ-5D-5L) will be used to assess five dimensions: mobility, self-care, usual activities, pain/discomfort and anxiety/depression.

8.2.2.3. COVID-19 8-Point Clinical Progression Outcomes Scale

Progression is assessed on COVID-19 8-point ordinal scale collected daily from randomization through Day 28, regardless of discharge or treatment discontinuation status, to adequately capture relevant COVID19 outcomes. Remote data collection methods, such as electronic data collection, phone, and telehealth assessments can be used after patient discharge from the hospital through Day 28 (see **Section 1.3**). The ordinal scale of patient health status ranges from: 1) Death; 2) Hospitalized, on invasive mechanical ventilation or extracorporeal membrane oxygenation (ECMO); 3) Hospitalized, on non-invasive ventilation or high flow oxygen devices; 4) Hospitalized, requiring supplemental oxygen; 5) Hospitalized, not requiring supplemental oxygen - requiring ongoing medical care (COVID-19 related or otherwise); 6) Hospitalized, not requiring supplemental oxygen - no longer requires ongoing medical care; 7) Not hospitalized, limitation on activities and/or requiring home oxygen; 8) Not hospitalized, no limitations on activities.

8.2.2.4. Pulse Oxygen Saturation (SpO2):

Measuring the amount of oxygen-carrying hemoglobin in the blood relative to the amount of hemoglobin not carrying oxygen will be done at the time points described in the Schedule of Activities (see Section 1.3).

8.2.2.5. Laboratory Assessment of Changes and Trend in Inflammatory Markers

Laboratory tests for IL-6 CRP, LDH, CPK, ferritin and D-dimer levels will be done at the time points described in the Schedule of Activities (see **Section 1.3**) to evaluate early markers of inflammation response. Laboratory tests will be performed locally, at CLIA certified local laboratory following the site's best practices.

CONFIDENTIAL Page 42 of 66

- Ferritin levels may be useful early markers of disease progression or dysregulated immune response.
- D-dimer level is associated with pro-inflammatory cytokine cascade and development of cytokine storm.
- CRP produced by the liver in response to IL-6 is a marker of inflammation and rapid increase of CRP level is a marker of increased risk of cytokine storm development.

8.2.2.6. **RT-PCR**

RT-PCR will be done at the time points described in the Schedule of Activities (see **Section 1.3**). At screening positive RT-PCR result (presence of SARS-COV-2 RNA) is required for inclusion criterion evaluation. Local, fully validated, RT-PCR tests shall be performed in a CLIA-certified and CAP-accredited laboratory.

8.2.2.7. Chest Radiograph or CT

Chest X-ray or chest CT will be done and evaluated locally according to the standard site practice at the time points described in the Schedule of Activities (see **Section 1.3**). Responses to CX-4945 administration will be followed on radiograph or CT scans using the Response Evaluation in COVID-19 patients with pneumonia. The chest-CT analysis will be performed considering number of pulmonary lesions, lesion's extend, number of pulmonary lobes affected, and common COVID-19 typical abnormalities like consolidation, glass-round opacity and mix pattern.

8.3. ADVERSE EVENTS AND SERIOUS ADVERSE EVENTS

The Investigator is responsible for the detection and documentation of events meeting the criteria and definition of an AE or SAE, as provided in this protocol. During the study when there is a safety evaluation, the Investigator or site staff will be responsible for detecting, documenting and reporting AEs and SAEs as detailed in this Section of the protocol.

8.3.1. Definitions of Adverse Event (AE)

An adverse event (AE) is defined as any unfavorable or unintended sign, symptom, or disease that occurs or is reported by the patient to have occurred, or a worsening of a pre-existing condition. An adverse event may or may not be related to the study treatment.

AEs will be elicited through direct questioning and subject reports. Any abnormality in physical examination findings or laboratory results that the investigator believes is clinically significant (CS) to the research subject and that occurred after initiation of the first study treatment will be reported as AEs. Abnormal findings that are NOT clinically significant should not be recorded as an AE.

8.3.2. Definition of Serious Adverse Events

CONFIDENTIAL Page 43 of 66

A SAE is defined as any AE that:

- Results in death
- Is life threatening (the subject is at immediate risk of dying from the adverse experience)
- Requires subject hospitalization or prolongs existing hospitalization
- Results in persistent or significant disability/incapacity
- Is a congenital anomaly/birth defect
- Important medical events that may not result in death, be life-threatening, or require hospitalization may be considered a serious adverse effect when, based upon appropriate medical judgment, they may jeopardize the subject or subject and may require medical or surgical intervention to prevent one of the outcomes listed in this definition.

8.3.3. Classification of an Adverse Event

8.3.3.1. Severity of Event

The guidelines outlined in CTCAE v5.0 will be used for assessing the intensity of the event. The general guidelines for assessing the AE grade appear below. Full guidelines may be obtained at http://evs.nci.nih.gov/ftp1/CTCAE.

Table 5. CTCAE v5.0 General Guidelines

Grade	Description
Grade 1	Mild; asymptomatic or mild symptoms; clinical or diagnostic observations only; intervention not indicated.
Grade 2	Moderate; minimal, local or noninvasive intervention indicated; limiting age-appropriate instrumental activities of daily living (ADL)*.
Grade 3	Severe or medically significant but not immediately life-threatening; hospitalization or prolongation of hospitalization indicated; disabling; limiting self-care ADL†.
Grade 4	Life-threatening consequences; urgent intervention indicated.
Grade 5	Death related to AE.

^{*}Instrumental ADL refer to preparing meals, shopping for groceries or clothes, using the telephone, managing money, etc. †Self care ADL refer to bathing, dressing and undressing, feeding self, using the toilet, taking medications, and not bedridden.

-Common Terminology Criteria for Adverse Events (CTCAE), v5.0: November 27, 2017

8.3.3.2. Causality Assessment

CONFIDENTIAL Page 44 of 66

AEs will be assigned a relationship (causality) to the study treatment. The Investigator will be responsible for determining the relationship between an AE and the study treatment. The type of event, organ system affected, and timing of onset of the event will be factors in assessing the likelihood that an AE is related to the study treatment. Relationship of AEs to study treatment will be classified as follows:

- 1. **Definitely related**: This category applies to those AEs that the Investigator feels are incontrovertibly related to the study treatment. An AE may be assigned an attribution of definitely related if or when it meets all of the following criteria: (1) it follows a reasonable temporal sequence from administration of the study treatment; (2) it could not be reasonably explained by the known characteristics of the subject's clinical state, environmental or toxic factors, or other modes of therapy administered to the subject; (3) it follows a known response pattern to treatment with the study treatment.
- 2. Probably related: This category applies to those AEs which, after careful medical consideration at the time they are evaluated, are felt with a high degree of certainty to be related to the study treatment. An AE may be considered probable if or when (must have three): (1) it follows a reasonable temporal sequence from administration of the study treatment. (2) It could not readily have been produced by subject's clinical state, environmental or toxic factors, or other therapies administered to the subject. (3) Disappears or is decreased upon discontinuation of the study treatment. (4) It follows a known response pattern to treatment with the study treatment.
- 3. Possibly related: This category applies to those AEs which, after careful medical consideration at the time they are evaluated, are judged unlikely but cannot be ruled out with certainty to the study treatment. An AE may be considered possible if or when (must have two): (1) it follows a reasonable temporal sequence from administration of the study treatment. (2) It could not readily have been produced by subject's clinical state, environmental or toxic factors, or other therapies administered to the subject. (3) Disappears or is decreased upon discontinuation of the study treatment. (4) It follows a known response pattern to treatment with the study treatment.
- 4. Remotely related: In general, this category can be considered applicable to those AEs which, after careful medical consideration at the time they are evaluated, are judged likely to be unrelated to the study treatment. An AE may be considered unlikely if or when (must have two):

 (1) it does not follow a reasonable temporal sequence from administration of the study treatment. (2) It could not readily have been produced by subject's clinical state, environmental or toxic factors, or other therapies administered to the subject. (3) Disappears or is decreased upon discontinuation of the study treatment. (4) It does not follow a known response pattern to treatment with the study treatment.
- **5.** Unrelated: This category applies to those AEs which, after careful consideration at the time they are evaluated, are clearly and incontrovertibly due to extraneous causes (disease,

CONFIDENTIAL Page 45 of 66

environment, etc.) and determined with certainty to have no relationship to the study treatment.

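### Two of the four criteria for Remotely related (Section 8.3.3.2) count evidence for the drug, so one adverse event can meet both the Definitely and the Remotely checklists

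*Combined protocol and SAP*

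**What the plan says.** Section 8.3.3.2 (Causality Assessment) defines five classes. The first four pair a short narrative with a checklist; Unrelated has a narrative only.

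- **Definitely related** applies when "it meets all of the following criteria": plausible timing, no reasonable alternative explanation, known response pattern.
- **Probably related**: "An AE may be considered probable if or when (must have three" of four criteria, which are plausible timing, no ready alternative cause, abatement on stopping, and known response pattern.
- **Possibly related**: "An AE may be considered possible if or when (must have two" of the same four. Its narrative covers events "judged unlikely but cannot be ruled out with certainty to the study treatment".
- **Remotely related** covers events "judged likely to be unrelated to the study treatment" and also needs two of four criteria. The first two begin "1) it does not follow a reasonable temporal sequence from administration of the study treatment. (2) It could not readily have been produced by" the patient's condition or other listed causes. The last two read "3) Disappears or is decreased upon discontinuation of the study treatment. (4) It does not follow a known response pattern to treatment".

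The section also says: "The Investigator will be responsible for determining the relationship between an AE and the study treatment". Section 3 lists relationship to treatment among the descriptors of the primary endpoint. Section 8.3.4 has causality recorded for each adverse event by reference to 8.3.3.2. Section 9.8.4.3 tabulates treatment-emergent events by the five classes.

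**The concern.** Criteria (1) and (4) of Remotely related are the negatives of their counterparts under Probably and Possibly, as a class for likely-unrelated events requires. Criteria (2) and (3) are not negated; they repeat the counterpart wording. The absence of another cause, and improvement when CX-4945 is stopped, therefore count towards calling the event unlikely to be related. That conflicts with the class's own narrative.

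At stake is the consistency of a named descriptor of the primary endpoint. Two investigators who apply the text as written could class the same event differently and each point to a checklist in support. The effect falls on that descriptor and on the by-causality table in Section 9.8.4.3. The all-causality tables in the same section do not depend on these classes. Nor does serious adverse event reporting under Section 8.3.5, which covers all such events.

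**Working it through.** The plan gives no figure on this point, so the check is of checklist logic.

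**Inputs (all from 8.3.3.2).** Code four yes/no features as 1 or 0: T = plausible timing, N = no other ready cause, D = abates on stopping, K = known response pattern. Let S = T + N + D + K.

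| Feature | Definitely (all three) | Probably (three) | Possibly (two) | Remotely as written (two) |
|---|---|---|---|---|
| Timing | T | T | T | not T |
| Other cause | N | N | N | **N** |
| Stopping | not used | D | D | **D** |
| Pattern | K | K | K | not K |

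Assumption: criterion (2) of Definitely, worded slightly differently, is the same feature N.

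**Formulas, with the thresholds read as minimums**

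- Definitely: T = N = K = 1
- Probably: S ≥ 3
- Possibly: S ≥ 2
- Remotely as written: (1 − T) + N + D + (1 − K) ≥ 2
- Remotely with (2) and (3) negated: (1 − T) + (1 − N) + (1 − D) + (1 − K) = 4 − S ≥ 2

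**Two test cases**

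- All four features present: Definitely is met 3 of 3. The Remotely score is 0 + 1 + 1 + 0 = 2, so Remotely is met as well. The score is exactly 2, so this holds whether the threshold means at least two or exactly two.
- Timing only: the Remotely score is 0 + 0 + 0 + 1 = 1, which fails. S = 1, so Probably and Possibly fail, and so does Definitely. Such an event has another ready cause, no abatement and no known pattern. It suits the Remotely narrative but meets just one of that class's criteria.

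**All 2⁴ = 16 profiles**

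| Reading | Wording | Remotely met | also Definitely | also Probably | also Possibly | No checklist met |
|---|---|---|---|---|---|---|
| At least | as written | 11 | 1 | 3 | 8 | 2 |
| At least | negated | 11 | 0 | 0 | 6 | 0 |
| Exactly | as written | 6 | 1 | 0 | 4 | 4 |
| Exactly | negated | 6 | 0 | 0 | 6 | 5 |

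- In the first row, the three overlaps with Probably are TNDK, TND and NDK; TNDK also meets Definitely. The two unmatched profiles are T only and K only.
- The unchanged 11 carries no information. Any at-least-two-of-four rule gives 6 + 4 + 1 = 11.
- In the second row, Probably needs S ≥ 3 and Remotely needs S ≤ 2, so they cannot coincide. Definitely implies S ≥ 3, so the same holds for it. Every S is either ≥ 2 or ≤ 2, so nothing is unmatched. The ties with Possibly are the profiles with S = 2, and there are six ways to choose two of four.
- In the last row, negation alone raises the unmatched profiles from 4 to 5 if the threshold is read as exactly. The words at least are therefore part of the fix.

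**CX-4945 not stopped.** D cannot be met, which leaves 8 profiles (at-least reading). As written, Remotely is met in 4. It overlaps Possibly in 2 and Probably or Definitely in 0, and 2 profiles are unmatched. With (2) negated and (3) not counted, Remotely is met in 4, with no overlaps and none unmatched. Every overlap with Probably or Definitely therefore needs abatement after CX-4945 is stopped. Taking study treatment in this section to mean CX-4945, these overlaps can arise in Arm A only, about 40 / 2 = 20 patients.

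**The case against.** The best defence is that the checklists are not binding. Each says an event may be considered to belong, the investigator decides, and the narratives already separate the extremes: no event can be both incontrovertibly related and likely unrelated. Suppose investigators always took the highest class met, at-least reading. The 16 profiles then fall as Definitely 2, Probably 3, Possibly 6, Remotely 3, unmatched 2 under the present wording, and 2, 3, 6, 5, 0 after correction. If the Remotely narrative absorbs the two unmatched profiles, no profile changes class. It is also true that overlap between adjacent classes is normal in a graded scale, so the missing words at least and the absence of a tie-break are refinements rather than contradictions.

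Most of this stands as a limit on consequence. It does not make the wording coherent, and the protocol states no highest-class rule.

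The limits also rule out stronger readings. A reader might infer that events strongly linked to CX-4945 will be recorded as remote and that drug-related toxicity will be under-reported. The documents do not support this: nothing forces that grade, and no share of events per profile is given. A reader might think the unmatched profiles cannot be classed at all; the narrative can still cover them. A reader might also connect the defect to Table 3 in Section 6.1.5, which is keyed to toxicity attributed to the drug. That table neither cites 8.3.3.2 nor says which classes count as attributable, so a link is neither shown nor excluded.

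**Conclusion.** This is an internal inconsistency in Section 8.3.3.2 and should be corrected. Criteria (2) and (3) of Remotely related contradict the class's own definition. The conflict between Definitely and Remotely exists under either reading of the threshold.

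Its size in checklist terms, at-least reading, is 3 of 16 profiles shared with Probably, 1 of them also with Definitely, and 2 matching no checklist. The profiles are unweighted and say nothing about how often such events occur. The result rests on treating the alternative-cause criterion as one feature across classes. The wording error is certain; the number of events affected cannot be derived from the documents. The case for acting is that causality is a primary-endpoint descriptor and the correction is small.

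**What to change.** In Remotely related:

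- Reverse criterion (2), so that it is met when the event could readily have arisen from the patient's condition or one of the other listed causes.
- Reverse criterion (3), so that it is met when the event neither resolves nor lessens after study treatment is stopped, and state that it is not counted if study treatment was not stopped.

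Write at least two for Possibly and Remotely, and at least three for Probably.

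The six ties with Possibly remain for the investigator to settle from the narratives, which are close to each other. No tie-break is proposed, because a highest-class rule would push those ties upward on a primary-endpoint descriptor.

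Apply the wording going forward. The cost is a short protocol correction, with IRB approval where Sections 11.2 and 12.1 require it, and a memo to sites. Events graded before and after the change will have used different wording. Any re-grading would be unblinded, since the trial is open-label (Section 9.5), so the grades already recorded should be kept.

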8.3.3.3. Expectedness

Medical Monitor will be responsible for determining whether an adverse event (AE) is expected or unexpected. An AE will be considered unexpected if the nature, severity, or frequency of the event is not consistent with the information described in the Investigator Brochure.

Refer to the Investigator Brochure for the expected/anticipated events.

CONFIDENTIAL Page 46 of 66

8.3.4. Reporting of Adverse Events

Report initiation for all AEs and SAEs will begin at the time of randomization and continue until the end of final study visit. All events will be followed to resolution or until the subject completes the study. A final assessment of outcome will be made at that time.

All AEs must be recorded in the subject's study records. AEs will be reported using customary medical terminology along with the following information: the onset and end dates, whether the event is considered to be a SAE (see Section 8.3.2), the impact the event had on study treatment (see Section 8.3.4.1), the Common Terminology Criteria for Adverse Events (CTCAE) grade (intensity) of the event (see Section 8.3.3.1), the causality of the event (see Section 8.3.3.2), whether treatment was given as a result of the event (see Section 8.3.4.2), and the outcome of the event. (see Section 8.3.4.3)

8.3.4.1. Impact on Study Treatment

The impact the event had on the study treatment will be assessed as either: dose increased, dose not changed, dose rate reduced, dose reduced, drug interrupted, drug withdrawn, not applicable, or unknown. The "not applicable" assessment will be used only when the subject is no longer in the Treatment Phase of the protocol.

8.3.4.2. Treatment Given as a Result of the Event

The event impact in terms of treatment provided will be as either: none, medication administered, non-drug therapy administered, surgery performed, hospitalization, or other (with a specification).

8.3.4.3. Outcome Assessment

The outcome of the event will be assessed as either: fatal, not recovered/not resolved, recovered/resolved, recovered/resolved with sequelae, recovering/resolving, or unknown. Only one AE per subject is allowed to have an outcome assessment as "death." If there are multiple causes of death for a given subject, only the primary cause of death will have an outcome of death.

8.3.5. Reporting of Serious Adverse Events (SAE)

The Investigator is required to report all SAEs that occur during the time period specified in **Section 8.3.4**. The sponsor or its designated representative shall be notified within 24 hours of the Investigator awareness of the event. In particular, if the SAE is fatal or life-threatening, notification to the sponsor must be made immediately, irrespective of the extent of available AE information. This time frame also applies to additional new information (follow-up) on previously forwarded SAE reports.

In the rare event that the investigator does not become aware of the occurrence of an SAE immediately (eg, if an outpatient study patient initially seeks treatment elsewhere), the investigator

CONFIDENTIAL Page 47 of 66

is to report the event within 24 hours after learning of it and document the time of his or her first awareness of the AE.

For all SAEs, the investigator is obligated to pursue and provide information to the sponsor in accordance with the time frames for reporting specified above. In addition, an investigator may be requested to obtain specific additional follow-up information in an expedited fashion. This information collected for SAEs is more detailed than that captured on the AE CRF. In general, this will include a description of the AE in sufficient detail to allow for a complete medical assessment of the case and independent determination of possible causality. Information on other possible causes of the event, such as concomitant medications, vaccines, and/or illnesses, must be provided. In the case of a patient death, a summary of available autopsy findings must be submitted as soon as possible to the sponsor or its designated representative.

The Investigator is also responsible for reporting all SAEs to the appropriate Institutional Review Board (IRB) in accordance with local laws and regulations. The Investigator is responsible for maintaining documentation in the study file that indicates the IRB has been properly notified.

8.3.6. **SAE Follow-Up**

All subjects experiencing an SAE, including the discontinued subjects, must be closely followed until sufficient information is obtained to indicate a return to normal status or until the event stabilizes at a level acceptable to the investigator (i.e., recovery, return to baseline status, no further improvement expected, or death).

For each SAE indicated as an unresolved event on the initial report, regardless of whether the subject completed the study or withdrew, the site should submit a follow-up report with updated information.

CONFIDENTIAL Page 48 of 66

